Finally, there were two slightly misplaced devices (up to one centimeter) at one New Zealand center noticed by the DSMB during review of photographs taken at the subjects’ healing check visits. An investigation was opened to determine how the misplacements occurred and to decide whether the center should continue implantations. The DSMB determined that the center had not used a measurement tool optimally. In response, the surgical trainer retrained the appropriate PI on this tool, updated and clarified the surgical manual, and communicated with all PIs on the correct use of the measurement tool. The DSMB was satisfied that actions taken would prevent further misplacements and allowed continued implantations at the affected center. The Sponsor believes that

Pivotal Study of Subcutaneous Tibial Nerve Stimulation with eCoin[®] for Urgency Urinary Incontinence.

proctoring of all first implants, as done in the United States where no misplacements occurred, provides assurance that all devices will be optimally placed.

In summary, the safety data suggest that the primary concern is mild to moderate wound healing, which resolved in all cases.

2-2-2-3 Safety of eCoin[™] Median Nerve Stimulation for Hypertension

The global multicenter feasibility study on hypertension is complete and thus the safety data are available for review and presented herein. Among the 48 subjects with 96 implanted eCoin[™] devices, two related Serious Adverse Events (SAEs) (called out as “SAE #1” and “SAE #2” in this Section) occurred.

Nine subjects have experienced inflammation tenderness or redness at the incision site or hand. Four subjects have been treated for an infection at the implant site. One of these infections occurred six months post implant and led to the explant of the device (SAE #1). Three of the four infections occurred at one clinical center which was subsequently shut down at the recommendation of the DSMB. One additional explant of a device occurred at this same center due to an unconfirmed infection (SAE #2). All remaining Adverse Events were judged to be unrelated to the device or therapy.

Attachment 4-12 presents the case report forms for the four reported infections. In addition, a fifth case report form is included for what the DSMB regarded as an infection leading to explant that was not appropriately handled by the center in Ottawa, Canada (Site 12).

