Pivotal Study of Subcutaneous Tibial Nerve Stimulation with eCoin[®] for Urgency Urinary Incontinence.

- While other device modalities are more invasive (i.e., sacral neuromodulation or botulinum toxin of the bladder) and drug therapy is fraught with poor compliance, as an investigational device, the study will only include patients who have an inadequate response to second or third line therapies.
- Some subjects may not receive clinical benefit from eCoin[™] therapy, but are to continue with follow-up until study completion even if they ask for eCoin[™] to be explanted. Some individuals who initially do not receive clinical benefit may benefit from late response and cumulative effects of treatment.
- Subjects are intended to be without pharmacological medications for overactive bladder. If the addition of medications is medically necessary as described herein, such information will be collected and reported.

3-4 Study Procedures

All subjects will be followed for 48 weeks post-activation (which is the same as 52 weeks post-implantation). A 3-day voiding diary will be collected that reports the number and type of incontinence episodes, number of micturitions; and administering questionnaires including the OABq, and PGI-I at 4, 8, 12, 24, 36, and 48 weeks post-activation.

The follow-up study visits are described in relationship to the initial activation visit occurring 4 weeks after implantation of the study device. Thus, 52 weeks post-implantation occurs at the 48 weeks post-activation visit, and 28 weeks post-implantation occurs at the 24 weeks post-activation visit. See Visit Overview 3-4-2 for exact timing of such visits. For any enrolled subject who is not activated, the same schedule will be followed as if the subject were activated.

All subjects are expected to remain free of pharmacological medications for overactive bladder, unless medically necessary, until the primary endpoint is measured at 48 weeks post-activation. Subjects who are taking pharmacologic medication at screening should be washed off OAB medications for a period of 2 weeks prior to the baseline visit.

All subjects will either be explanted after the study visit at 48 weeks post-activation, or, if they consent to extended follow up, they will be explanted shortly after their 96 week post-activation visit or their 144 week post-activation visit.

COVID-19 Considerations

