The Sponsor's feasibility study for which the study device, eCoin[™], was implanted in 46 subjects showed a benign safety profile. In particular, no infection at the implant site occurred that required explant. At the time of this writing, all subjects have been followed for at least six months since implantation of the study device. Given that the primary safety concern is infection and that all serious infections are expected to occur by one month after implantation, the adverse event information compiled thus far is promising. Three serious adverse events (SAEs) have occurred: one unrelated pneumonia incident, one unrelated limp due to underlying bursitis of the hip present at screening, and one related cellulitis of the calf secondary to the ankle support suggested as post-operative care. See Attachment 04-32 for additional information on safety. Furthermore, given the expected therapeutic similarity of percutaneous nerve stimulation of the tibial nerve to eCoin[™] stimulation of the tibial nerve, the therapy is not expected to cause adverse events. Nonetheless, safety will be reported through adverse event reporting for the study duration.

While an important benefit to the eCoin[™] system is that delivery of therapy does not require the patient to operate a percutaneous device and locate the tibial nerve on a regular basis, it is also important to understand how well patients tolerate the device. In order to assess patient acceptance, a patient satisfaction grade will be documented for each subject at all follow-up visits.

32. Wagner, T. H., et al. "Quality of life of persons with urinary incontinence: development of a new measure." *Urology* 47.1 (1996): 67-71.
33. Hajebrahimi, Sakineh, et al. "Validity and reliability of the International Consultation on Incontinence Questionnaire-Urinary Incontinence Short Form and its correlation with urodynamic findings." *Urology journal* 9.4 (2012): 685.

3-7 Risk Analysis

3-7-1 Overview

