Device-related risks of the eCoin[™] system can be deduced from the 50 year field of neuromodulation. The primary risks of importance are infection and lead-related problems (e.g., leadwire break or migration). For the leadless eCoin[™] system, lead-related problems are not relevant. Reasonable estimation of the rate of infection can be based upon other neuromodulation devices, the sponsor's feasibility study testing eCoin[™] for hypertension, and the sponsor's feasibility study testing eCoin[™] for OAB. Infection can be mitigated through surgical training, adequate manufacturing controls, and adequate after-care instructions. Infection can be resolved through antibiotics generally and, in a worst case scenario, explantation of eCoin[™].

Pivotal Study of Subcutaneous Tibial Nerve Stimulation with eCoin[®] for Urgency Urinary Incontinence.

If needed, explantation of the eCoin[™] device can be performed easily through simple opening of the capsule and removal of the device. If the capsule itself has a significant problem such as deep infection or dense scar tissue causing significant discomfort, then the capsule might require surgical excision, a procedure known as capsulectomy.

In the ongoing clinical study of eCoin[™] for OAB conducted under an IDE, no patient required explant due to infection. One cellulitis of the calf secondary to the ankle wrap occurred where the patient chose to have the device explanted prior to activation of the device. The aforementioned safety data are current as of the date of this writing at which time all patients have been followed at least six months from implantation. See Attachment 04-28 for a table on reported related adverse events. In the OUS clinical study of eCoin[™] for hypertension, the proportion of infection requiring explant, on a per patient basis was approximately 4.2%. See [Subsection 2-2-2-1](#) and [2-2-2-2](#) for details on the adverse events that occurred during both studies.

The eCoin[™] utilizes established biocompatible materials and manufacturing processes that are typical of implantable neurostimulators (titanium hermetic enclosure, silicone elastomer insulation coating (MED-4870) and with platinum stimulating electrodes).

3-7-5 Standards Conformance Demonstrating Safety

The eCoin[™] system has been developed under design control in accordance with QSR 21 820.30 and ISO 13485.

3-7-5-1 Risk Management

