The study can be terminated at any time for any reason by Valencia Technologies. Should this be necessary, the subjects should be seen as soon as possible and treated as described in the early withdrawal section for a prematurely withdrawn subject. The Investigator may be informed of additional procedures to be followed in order to ensure that adequate consideration is given to the protection of the subjects' interests. The Investigator will be responsible for informing the IRB of the early termination of the trial. If required, provisions for the explant of the eCoin[™] system will be arranged.

3-8-7-5 Data Collection and Follow-up for Withdrawn Subjects

Subjects who are not implanted with the eCoin study device will not be followed after termination or withdrawal from the study.

3-8-8 COVID-19 Related Delayed Explantation

Subjects who do not or did not consent to extended follow up may have an explant well beyond the final study visit window because of COVID-19 considerations. However, the database may be locked through the 48 week final study visit following complete monitoring. Subjects who do not or did not consent to extended follow up will not undergo study procedures beyond those originally consented but will continue to be followed for adverse events and complaints until explantation is performed and healing is observed. This will be done under the extension portion of this protocol.

3-8-9 Data and Safety Monitoring Board

A Data and Safety Monitoring Board of at least three members will review data including a quarterly report of Adverse Events. This DSMB will meet by telephone monthly until all subjects reach one month post-implantation and at least quarterly until all subjects reach 52 weeks post-implantation to review aggregate and individual subject data related to safety, data integrity, and overall conduct of the trial. The DSMB will be responsible for reviewing adverse events. The DSMB will provide recommendations to continue or terminate the trial depending upon this review. A DSMB charter is set forth in a DSMB Charter document (see 4-10).

Pivotal Study of Subcutaneous Tibial Nerve Stimulation with eCoin[®] for Urgency Urinary Incontinence.

3-9 Data Analysis Plan

3-9-1 Data Collection

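### Scheduled DSMB meetings end once all subjects reach 52 weeks after implant, although extended follow-up keeps devices in place to 96 or 144 weeks after activation and then removes them surgically

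*Protocol*

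**What the plan says.** Section 3-8-9 of the protocol sets the DSMB's meetings: "monthly until all subjects reach one month post-implantation and at least quarterly until all subjects reach 52 weeks post-implantation". At these meetings the board looks at pooled and individual data on safety, data integrity and conduct, and it advises whether the trial should go on. The SAP contains no DSMB schedule.

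Follow-up runs well past that point. Under section 3-4 the default is explant after the 48-week visit, but for subjects who agree to extended follow-up, "they will be explanted shortly after their 96 week post-activation visit or their 144 week post-activation visit". Section 3-4-2 gives the visit windows, the explant visit and a healing check after explant. Section 3-8-8 allows COVID-delayed explants well outside the normal window and places their adverse-event follow-up, until healing, in the extension. Section 3-9-3-2 item 7 and SAP section 5.7 define the population for safety and effectiveness analyses at 2 and 3 years.

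On infection timing, section 3-6 states that "all serious infections are expected to occur by one month after implantation". Section 2-2-2-3, on the hypertension study of the same device, reports: "One of these infections occurred six months post implant and led to the explant of the device".

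**The concern.** Exposure, surgery, adverse-event collection and planned safety analyses were all extended beyond week 52. The board's meeting schedule was not. This looks like an amendment that was not carried through to section 3-8-9.

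What lapses is the pooled view and the formal advice. In this device programme the board's review has led to action: section 2-2-2-3 reports that three of four treated implant-site infections in the hypertension study came from one center, which was shut down on the DSMB's recommendation. The account of the overactive-bladder feasibility study, just before that section, says the DSMB noticed two misplaced devices from healing-check photographs. The extension also produces photographs, at explant and at the post-explant check, and it contains explant surgery, but no scheduled meeting covers it.

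**Working it through.** The point rests on visit timing, so the check is calendar arithmetic from the protocol's own windows.

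**Inputs**
- Meetings are required until the last subject reaches 52 weeks (364 days) after implant (3-8-9).
- Activation is nominally 4 weeks after implant, window 23-43 days (3-4-2, Visit 5).
- Visit 11 is 331-341 days and Visit 13 is 998-1,018 days after activation. Explant is 0-15 days after the relevant visit, and the healing check 9-19 days after explant (3-4-2).
- Planned start is July 2018 and planned end of enrollment March 2019 (3-12).

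**1. Last-implanted subject, nominal weeks.** Weeks after implant = weeks after activation + 4.
- Explant after week 144: 144 + 4 = 148 device weeks; 148 - 52 = 96 without a scheduled meeting; 96/148 = 65%.
- Explant after week 96: 96 + 4 = 100 device weeks; 100 - 52 = 48; 48/100 = 48%.
- At the widest windows, explant can fall on day 43 + 1,018 + 15 = 1,076 after implant and the healing check on day 1,076 + 19 = 1,095 (week 156.4). The uncovered share is then (1,076 - 364)/1,076 = 712/1,076 = 66%. That figure is an upper limit.

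**2. First-implanted subject.** Meetings continue until the last subject reaches week 52, so early subjects are covered for longer. Assume implants span the planned enrollment period: 30.4 weeks (31 July 2018 to 1 March 2019) to 39 weeks (1 July 2018 to 31 March 2019).
- Meetings reach this subject's week 52 + 30.4 = 82.4 to 52 + 39 = 91.
- Stay to week 144: 148 - 91 = 57 to 148 - 82.4 = 65.6 weeks uncovered, or 39-44% of 148.
- Stay to week 96: 100 - 91 = 9 to 100 - 82.4 = 17.6 weeks uncovered, or about 9-18% of 100.

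**3. Default explant, last-implanted subject.** The latest explant is day 43 + 341 + 15 = 399 and the latest healing check day 399 + 19 = 418. These are 35 and 54 days after day 364. Even without the extension, the last explants and healing checks can therefore fall after the last scheduled meeting.

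**4. Infection statements side by side.** Section 3-7-4-3 puts infection requiring explant in the hypertension study at about 4.2% per patient. Two such explants among 48 subjects give 2/48 = 4.17%, which reproduces it. One of the two arose at six months: 1/48 = 2.1% (exact 95% interval 0.05% to 11.1%). Section 3-7-4-3 lists, among its sources for estimating infection risk, "the sponsor's feasibility study testing eCoin[™] for hypertension, and the sponsor's feasibility study testing eCoin[™] for OAB", so the protocol treats these data as relevant. The overactive-bladder feasibility study had no implant-site infection requiring explant in 46 subjects followed at least six months. The upper end of the exact 95% interval for 0/46 is 7.7%, so it does not rule out late infection.

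**The case against.** The strongest defence is that safety review does not stop at week 52. Every adverse event goes to a reviewer who sits on the DSMB or is appointed by it, with no end date (3-8-6-4). Serious events get medical review within 24 hours, and the sponsor notifies investigators across centers (3-8-6-5). Collection runs to final follow-up (3-8-6-6). Section 3-8-9 itself refers to a quarterly adverse-event report and gives the board responsibility for adverse events, without a time limit on either. The charter (Attachment 4-10) is not reproduced and may cover the extension. Finally, the title of Attachment 4-13 refers to suspending implantation at a site, and by week 52 of the last subject no first implants remain to suspend.

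Much of this stands. It rules out any claim that late events would go unseen, and it weakens the analogy with the hypertension cluster. It does not supply a scheduled pooled review or a recommendation on continuing, which are the functions section 3-8-9 attaches to the meetings. If the charter does cover the extension, section 3-8-9 still needs to match it.

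A reader might infer three stronger points that the documents do not support.
- **That monthly review stops after one month.** It runs until one month after the last implant, about 35-43 weeks from the first under the enrollment assumption above. Later meetings are at least quarterly, so month six falls within the scheduled meeting period for every subject.
- **That the cadence was built on the one-month infection expectation.** No section links the two.
- **That late events are a known share of infections or related serious events.** The late event is one subject of 48, at a median-nerve site. Section 2-2-2-3 gives no onset times for the other infections or for the second related serious event.

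**Conclusion.** The point holds as a gap in a stated rule. No DSMB meeting is scheduled for extended follow-up, for its explants or for COVID-delayed explants falling after the last subject's week 52. The uncovered share of nominal device time is 65% (three-year option) or 48% (two-year option) for the last-implanted subject. For the earliest-implanted subjects it is about 39-44% or 9-18% respectively.

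The figures for early subjects assume that implants span 30-39 weeks, taken from planned dates. The documents do not say how many subjects enter the extension, so the number affected cannot be given. Staying beyond week 48 is by consent, and whether a device is still stimulating at week 144 depends on a battery described in section 3-8 as typically lasting 2 to 4 years.

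The conflict between sections 3-6 and 2-2-2-3 is a separate and smaller matter. It concerns the accuracy of a stated expectation and does not create the meeting gap. This is an inexpensive improvement to safety oversight; it does not affect the primary analysis.

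**What to change.** In section 3-8-9, move the end of scheduled DSMB meetings from the last subject's week 52 to the point when the last subject has completed the post-explant healing check, expressly including extended follow-up and COVID-delayed explants. State the cadence after week 52; it may be lower than quarterly, and the choice can be left to the sponsor and the board. Confirm that the charter says the same.

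Separately, reconcile the one-month infection statement in section 3-6 with the six-month infection in section 2-2-2-3, for example by limiting the statement to the study it describes or by acknowledging the later event.

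The cost is protocol wording, charter wording if it differs, and a few extra teleconferences of an existing board. No subject procedures or data collection are added.
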